Study Endpoints:	
Primary Efficacy Endpoint
 
Two co-primary endpoints will be evaluated in the trial:
 
 • Change from baseline in the expression of IFN-induced genes at Week 36. • Response to treatment with IFN-K as measured by the British Isles Lupus Assessment Group (BILAG)-based Composite Lupus Assessment (BICLA) response criteria at Week 36: 
 - All BILAG A scores at baseline improve to B/C/D and all BILAG B scores improve to C/D at Week 36 and - No BILAG worsening in other body systems: no new BILAG A or \geq 2 new BILAG B scores at Week 36 and - No worsening in SLEDAI-2K total score at Week 36 compared with baseline and - No deterioration in PGA (< 10% worsening) on VAS 100 mm at Week 36 compared with baseline and - No addition or increased dose level of anti-malarial drugs or immunosuppressive drugs or corticosteroids between Week 24 and Week 36 
Secondary Endpoints
 
Clinical secondary Endpoints
 
 • Response to treatment with IFN-K, as measured by the SLE Responder Index (SRI)-4 response criteria at Week 36: 
 - Reduction \geq 4 points in SELENA-SLEDAI and - No new BILAG A and - No more than 1 new BILAG B and - No deterioration in PGA (< 10% worsening) on VAS 100 mm compared with baseline • Response to treatment with IFN-K, as measured by SLEDAI response, defined as a reduction of the SLEDAI-2K score of at least 4 points at Week 36 compared to baseline • Response to treatment with IFN-K, as measured by BILAG grade changes by body system • Response to treatment with IFN-K, as measured by incidence of SLE flare (SELENA SLEDAI flare index, BILAG flares)

	
• Response to treatment with IFN-K, as measured by SLICC/ACR-DI• Response to treatment with IFN-K, as measured by Cutaneous LE Disease Area and Severity Index (CLASI)
	
Immunogenicity secondary Endpoints
 
At timepoints specified on the flow chart, Geometric Mean Titers (GMT) and seroconversion rates for:
 
• Anti-IFNα binding antibody titers• Anti-IFNα neutralizing antibody titers• Anti-KLH binding antibody titers

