10.7.2 Medications leading to study product discontinuation

The following medications will result in study product discontinuation. As described in Section 10.6.3, the patient should however continue other study procedures until Week 36 for the primary analysis and as much as possible in the Extended Follow up if applicable.

- Pulse dose CS (≥ 250 mg prednisone equivalent/day)
- Potent immunosuppressive drugs such as cyclophosphamide, cyclosporine A, oral tacrolimus
- Biological disease modifying products, including belimumab, anti-IFN monoclonal antibodies
- Anti-B-Cell therapy, such as rituximab (RTX) and epratuzumab,
- Any investigational or non-registered product (drug or vaccine) other than the study product
- Any live vaccine (e.g., nasal influenza vaccine, oral poliomyelitis vaccine, measles-mumps-rubella vaccine, yellow fever vaccine, Japanese encephalitis vaccine, dengue vaccine, rotavirus vaccine, varicella vaccine, zoster vaccine, BCG, oral typhoid vaccine)

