4.1.2 Secondary efficacy endpoints

4.1.2.1 Clinical Secondary Endpoints

- Response to treatment with IFN-K, as measured by the SLE Responder Index (SRI)-4 response criteria at Week 36:
 - Reduction \geq 4 points in SELENA-SLEDAI at week 36 compared with baseline
and
 - No new BILAG A at Week 36
and
 - No more than 1 new BILAG B at Week 36
and
 - No deterioration at Week 36 in PGA (< 10% worsening) on VAS 100 mm compared with baseline
- Response to treatment with IFN-K, as measured by the composite SLE Responder Index (SRI)-4 response criteria at Week 36:
 - Same criteria as above
and
 - Sustained reduction in oral corticosteroids (\leq 5 mg and \leq 7.5mg/day) at Week 36 (these criteria will be identified by medical review)
- Response to treatment with IFN-K, as measured by SLEDAI response, defined as a reduction of the SLEDAI-2K score of at least 4 points at Week 36 compared to baseline
- Response to treatment with IFN-K, as measured by BILAG grade changes by body system
- Response to treatment with IFN-K, as measured by Incidence of SLE flare (SELENA SLEDAI flare index. BILAG flares)
- Response to treatment with IFN-K, as measured by SLICC/ACR-DI
- Response to treatment with IFN-K, as measured by Cutaneous LE Disease Area and Severity Index (CLASI)
- Response to treatment with IFN-K, as measured by LLDAS (Franklin *et al*, 2016)

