5.2.4.3 Secondary efficacy analyses

Secondary efficacy analyses will be performed on the FAS population except if otherwise specified.

5.2.4.3.1 *SRI response*

The SRI-4, 6, 8, 10 responses will be described at Week 36. (Statistical tables 14.2.5.1, 14.2.5.4, 14.2.6.1, 14.2.7.1, 14.2.8.1)

The SRI-4 response (section 4.1.2.1) will be analyzed using the same method as the primary analysis for the second co-primary endpoint (logistic regression). This analysis will be performed both on the FAS and PP sets. (Statistical tables 14.2.5.2 & 14.2.5.5)

The model on FAS for patients IFN-K treated with the status of IFN α neutralizing antibodies (positive/negative) at Week 36 as dependent variable will be also presented (Statistical table 14.2.5.3).

The SRI-6, 8, 10 responses to treatment at week 36 will also be analyzed using a logistic regression using the response rate as dependent variable and treatment as independent variable, while adjusting for the minimization factors used for randomization. (Statistical tables 14.2.6.2, 14.2.7.2, 14.2.8.2)

All analyses performed on SRI-4 will also be conducted on the composite SRI-4 (both with tapering CS \leq 5 mg and \leq 7.5 mg) on the FAS population only. (Statistical tables 14.2.5.6 to 14.2.5.11)

The SRI-4 response is an important and alternative endpoint assessing the clinical response. In case, there will be no trend on the BICLA response, the SRI-4 response could be chosen as primary endpoint for further development of IFN-K.

5.2.4.3.2 *SLEDAI response*

Number of patients achieving a SLEDAI response, defined as a reduction of the SLEDAI-2K score of at least 4 points at Week 36 compared to baseline will be analyzed using frequency table methods (Statistical table 14.2.9).

SLEDAI-2K score at each visit and change from baseline by treatment group will also be presented (Statistical tables 14.2.10.1 to 14.2.10.2).

All SLEDAI data will be listed in Listing 16.2.6.2.

5.2.4.3.3 *BILAG*

Shift tables between Baseline and LVA (last available value between Week 36 and Week 24) will also be presented for each body system. (Statistical table 14.2.11)

Finally, descriptive statistics for the BILAG global score at each visit and change from baseline to LVA will be presented. The difference between treatment groups for the change from baseline to LVA will be analyzed using the non-parametric Wilcoxon-test. (Statistical table 14.2.12)

Statistical Analysis Plan

Study Name: IFN-K-002

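### SRI-4 has no medication component, so a full-analysis-set patient whose lupus drugs are added or increased in Weeks 24-36 fails BICLA but can count as an SRI-4 responder

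*Protocol*

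**What the plan says.** **SRI-4.** The protocol (Synopsis and 13.3.1) lists "Response to treatment with IFN-K, as measured by the SLE Responder Index (SRI)-4 response criteria at Week 36" as a clinical secondary endpoint. There and in SAP 4.1.2.1 it has the same four components: a fall of at least 4 "points in SELENA-SLEDAI at week 36 compared with baseline"; no new BILAG A; "No more than 1 new BILAG B at Week 36"; and a PGA that has not deteriorated by 10% or more. SRI-6, -8 and -10 are analysed alongside (protocol 13.9.3, SAP 5.2.4.3.1), and no medication condition is given for them either.

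**BICLA.** Protocol 13.2 and SAP 4.1.1 add to the activity components the condition "No addition or increased dose level of anti-malarial drugs or immunosuppressive drugs or corticosteroids between Week 24 and Week 36". SAP 4.1.1 says that medical review identifies it.

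**Composite SRI-4.** SAP 4.1.2.1 adds "Sustained reduction in oral corticosteroids", with ceilings of 5 and 7.5 mg/day at Week 36, also by medical review. SAP 5.2.4.3.1 states "All analyses performed on SRI-4 will also be conducted on the composite SRI-4", on the FAS only.

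**Role of SRI-4.** SAP 5.2.4.3.1 calls SRI-4 an important alternative measure of clinical response. If BICLA shows no trend, "the SRI-4 response could be chosen as primary endpoint for further development of IFN-K".

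**Patients who receive other drugs.** Under protocol 10.7.2 certain drugs end study product, but "the patient should however continue other study procedures until Week 36 for the primary analysis". The FAS (SAP 3.3.1) keeps every randomized patient who was dosed.

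**The concern.** BICLA and SRI-4 treat the same event differently. Take a patient who flares at Week 28, has an immunosuppressant added and is better at Week 36. BICLA records a failure. SRI-4 looks only at activity scores and can record a response, which then reflects the added drug as well as the allocated treatment.

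SRI-4 would be relied on in the case where BICLA has shown no trend. If the two indices then disagree, the reader needs to know whether SRI-4 picked up something about IFN-K or merely forgave added treatment. More intensification on placebo would narrow the SRI-4 difference; more on IFN-K would widen it.

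**Working it through.** **1. Does any rule in the plan already close the gap?**

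| Place | What it does | Makes an intensified FAS patient an SRI-4 non-responder? |
|---|---|---|
| SAP 9, SELENA-SLEDAI derivation | Sums the descriptor weights; the drug items in protocol Appendix 4 belong to the flare index | No |
| SAP 5.3.2, missing data | Imputes questionnaire items and dates; nothing on added medication | No |
| SAP 3.1.1, forbidden medication | May remove the patient from the per-protocol (PP) set | No: exclusion is not failure, and the FAS is unaffected |
| SAP 4.1.2.1, composite SRI-4 | Oral corticosteroid condition | For the composite only, and only for corticosteroids |
| SAP 5.2.4.5.4, treatment failure | Separate exploratory table, corticosteroids only | No |
| SAP 7.2.2 | Drops the analysis of changes in lupus therapy as redundant with BICLA and LLDAS | No |

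The gap is therefore real in the FAS analysis. For plain SRI-4 it covers antimalarials, immunosuppressants and corticosteroids. For the composite it covers mainly the first two.

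**2. Reproduce the plan's own figure.** Protocol 13.1 gives 73% power for BICLA at 20.6% vs 40.6%, with 80 evaluable patients per group and two-sided 5%. The pooled-variance formula is

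power = Φ{ [ |p1 − p0|·√n − 1.96·√(2p̄(1 − p̄)) ] / √(p0(1 − p0) + p1(1 − p1)) }, with p̄ = (p0 + p1)/2.

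Here p̄ = 0.306, and [0.200 × 8.944 − 1.96 × 0.6517] / 0.6362 = 0.804, so power is 78.9%. With a continuity correction it is 73.5%, which matches the stated 73%. The illustration below uses the uncorrected formula, so its reference value is 79%.

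**3. Illustrate the effect on SRI-4.** All of these inputs are assumptions except the BICLA planning rates, the group size and the 5% level:
- response without intensification: 20.6% placebo, 40.6% IFN-K (BICLA planning rates, borrowed because no SRI-4 rate is given);
- intensified in Weeks 24-36: 10-20% of placebo, 5-10% of IFN-K;
- share of intensified patients who meet the four components: 40-60%.

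SRI-4 rate in an arm = rate without intensification + (share intensified × share of these meeting the components).

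| Placebo / IFN-K intensified | Share responding | SRI-4 rates | Difference (points) | Power |
|---|---|---|---|---|
| none | – | 20.6 vs 40.6% | 20 | 79% |
| 10% / 10% | 40% | 24.6 vs 44.6% | 20 | 76% |
| 10% / 10% | 60% | 26.6 vs 46.6% | 20 | 75% |
| 10% / 5% | 40% | 24.6 vs 42.6% | 18 | 68% |
| 10% / 5% | 60% | 26.6 vs 43.6% | 17 | 62% |
| 20% / 10% | 40% | 28.6 vs 44.6% | 16 | 56% |
| 20% / 10% | 60% | 32.6 vs 46.6% | 14 | 44% |
| 20% / 5% | 40% | 28.6 vs 42.6% | 14 | 46% |
| 20% / 5% | 60% | 32.6 vs 43.6% | 11 | 30% |

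In the last row, placebo is 20.6 + 20 × 0.6 = 32.6 and IFN-K is 40.6 + 5 × 0.6 = 43.6. Across the corners the difference is 11-20 points and power 30-76%.

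**The case against.** **Most of these drug changes are already off-protocol.** Protocol Table 4 allows no corticosteroid increase from Week 12 to Week 36, no initiation of antimalarials, methotrexate, azathioprine or MMF, and only stable antimalarial doses. This stands, and it may keep the numbers small. It does not settle the matter: Table 4 does not expressly bar an increase of methotrexate, azathioprine or MMF below its ceiling in Weeks 24-36, the BICLA component presupposes that such cases occur, and a deviation in the FAS is not a failure.

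**Other outputs would show an imbalance.** SRI-4 is repeated on the PP set, prohibited medications are tabulated by arm (SAP 5.2.3), and treatment failure is tabulated. The composite's requirement of a sustained reduction could also fail a corticosteroid increase. This stands as mitigation, but none of it changes the FAS SRI-4 result.

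**Scoring added drugs as failure is an estimand choice.** True. The documents do not contradict themselves in defining SRI-4 by four components. The argument is that an endpoint held in reserve for BICLA should handle added treatment as BICLA does, or at least be shown both ways.

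**Stronger readings that the documents do not support.** A reader might infer that SRI-4 takes over as primary endpoint in this trial. SAP 5.2.4.3.1 only says that it could be chosen for later development, and a later protocol would set its own rules. A reader might also infer an inflated false-positive rate. With no treatment effect in a randomized, double-blind trial, intensification is equal between arms in expectation, so inflation appears only if an imbalance is assumed. Finally, a reader might want every drug in protocol 10.7.2 at any time before Week 36 counted as failure. That list includes live vaccines and investigational products, and the rule would go beyond the BICLA window.

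**Conclusion.** The concern holds as a gap in the definition of SRI-4, -6, -8 and -10 and, for non-steroid drugs, of the composite SRI-4. It is established by comparing the definitions and needs no numerical assumption. The success rule of this trial (gene signature plus a BICLA trend) is untouched; what is exposed is the reading of SRI-4 if BICLA disappoints.

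The size is unknown. The range found above rests on assumed intensification rates and on BICLA planning rates applied to a different index. Equal intensification leaves the difference unchanged and costs little power. Only unequal intensification distorts the difference, and the direction cannot be known in advance. This is a worthwhile low-cost improvement, not a threat to the primary analysis.

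**What to change.** In SAP 4.1.2.1 and 5.2.4.3.1, before unblinding, define SRI-4, SRI-6, SRI-8, SRI-10 and both versions of the composite SRI-4 as non-response for any patient who fails the BICLA Week 24-36 medication component. Use the flag that medical review already produces for BICLA, and add no wider drug rule. Report the four-component SRI-4 alongside as a supportive table, so that the effect of the rule is visible.

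The cost is a few lines of SAP text, one existing flag in the SRI derivation and the supportive table. No new data are needed. The downside is that SRI rates will be somewhat lower and will differ from the four-component index, which the supportive table covers.

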4. LIST OF ABBREVIATIONS

°C	Degrees Celsius
ACR	American College of Rheumatology
ACS	American Cancer Society
AE	Adverse Event
ALT	Alanine aminotransferase
ANA	Anti-Nuclear Antibodies
ANCOVA	Analysis of Covariance
Anti-RNP	Anti-Ribonucleoprotein
Anti-SSA	Anti-Sjögren's-syndrome A
Anti-SSB	Anti-Sjögren's-syndrome B
APECED	Autoimmune polyendocrinopathy-candidiasis-ectodermal dystrophy
AST	Aspartate aminotransferase
AZA	Azathioprine
BCG	Bacillus Calmette-Guérin vaccine
BICLA	British Isles Lupus Assessment Group-based Composite Lupus Assessment
BILAG	British Isles Lupus Assessment Group
CA	Competent Authorities
CI	Confidence Interval
CIN	Cervical intraepithelial neoplasia
CLASI	Cutaneous Lupus Erythematosus Disease Area and Severity Index
CMV	Cytomegalovirus
CPK	Creatine PhosphoKinase
CQ	Chloroquine
CRA	Clinical Research Associate
CrCl GFR	Creatinine Clearance (Glomular Filtration Rate)
CRO	Contract Research Organization
CRP	C-Reactive Protein
CS	Corticosteroid
CVS	Cardio Vascular System
CXCL	Chemokine (C-X-C motif) ligand
DNA	Deoxyribonucleic acid
dsDNA	Double-stranded DNA
DSUR	Development Safety Update Report
EBV	Epstein Barr Virus

EC	Ethics Committee
ECG	Electrocardiogram
eCRF	Electronic Case Report Form
EDC	Electronic Data Capture
eGFR	Estimated Glomerular Filtration Rate
FACIT	Functional Assessment of Chronic Illness Therapy
GCP	Good Clinical Practice
GLP	Good Laboratory Practice
GMP	Good Manufacturing Practice
GMT	Geometric Mean Titer
HIA	Hemagglutination Inhibition Assay
HBsAg	Hepatitis B surface Antigen
HBV	Hepatitis B Virus
hCG	human Chorionic Gonadotropin
HCQ	Hydroxychloroquine
HCV	Hepatitis C Virus
Hg	Mercury
HIV	Human Immunodeficiency Virus
HPV	Human Papillomavirus
HSIL	High Grade Squamous Intraepithelial Lesions
HSV	Herpes Simplex Virus
huIFN-α	Human interferon α
IB	Investigator's Brochure
ICF	Informed Consent Form
ICH	International Conference on Harmonization
iDSMB	Independent Data and Safety Monitoring Board
IEC	Independent Ethics Committee
IFN	Interferon
IFN-K	Interferon α -kinoid
Ig	Immunoglobulin
IL	Interleukin
IM	Intramuscular
IND	Investigational New Drug
INR	International Normalized Ratio
IRB	Institutional review board
ITT	Intention-to-treat
IUD	Intrauterine Device

IUS	Intrauterine system
IV	Intravenous
IWRS	Interactive Web Response System
KLH	Keyhole Limpet Hemocyanin
Mcg	micrograms
MCID	Minimum Clinically Important Difference
MCS	Mental Component Summary
MedDRA	Medical Dictionary for Regulatory Activities
 mL	milliliter
 mm	millimeter
MMF	Mycophenolate mofetil
MTX	Methotrexate
muIFN-K	Murine Interferon-Kinoid
NSAID	Non-Steroidal Anti-Inflammatory Drug
PBMCs	Peripheral Blood Mononuclear Cells
PCS	Physical Component Summary
PGA	Physician Global Assessment
PI	Principal Investigator
PP	Per Protocol
PT	Prothrombin time
PTT	Partial Thromboplastin Time
RBC	Red Blood Cell
Rhu	Recombinant human
mRNA	Messenger ribonucleic acid
RNP	Ribonucleoprotein
RTX	Rituximab
SAE	Serious Adverse Event
SAP	Statistical Analysis Plan
SAS®	Statistical Analysis System
SC	Subcutaneous
SELENA	Safety of Estrogen in Lupus Erythematosus National Assessment
SF-36	Short Form-36
SJC	Swollen Joint Count
SLE	Systemic Lupus Erythematosus
SLEDAI	Systemic Lupus Erythematosus Disease Activity Index-2000
SLICC/ACR-DI	Systemic Lupus International Collaborating Clinics/American College of Rheumatology Damage Index for Systemic Lupus Erythematosus

Sm	Smith antigen
SOP	Standard Operating Procedures
SP	Safety Population
SS	Sjögren's Syndrome
SUSAR	Suspected Unexpected Serious Adverse Reaction(s)
TJC	Tender Joint Count
TNF	Tumor Necrosis Factor
UCP	Urine C-peptide creatinine
VAS	Visual Analog Scale
WBC	White Blood Cell
WHO	World Health Organization
WMA	World Medical Association

5. BACKGROUND AND RATIONALE

5.1 Introduction

Systemic Lupus Erythematosus (SLE) is a chronic systemic autoimmune disease that can affect virtually any part of the body (Tsokos, 2011). Like in other autoimmune diseases, the immune system attacks the body's self-cells and tissues, resulting in inflammation and tissue damage. The course of the disease is unpredictable, with periods of illness (called flares) alternating with remissions. There is no definitive cure for SLE. The disease is currently treated with immunosuppression, mainly with hydroxychloroquine, cyclophosphamide, corticosteroids (CS) and other immunosuppressive drugs, all accompanied with significant debilitating side effects. Kinoids may offer an alternative treatment by induction of self-polyclonal antibodies anti-IFN α . IFN α -Kinoid has been evaluated in SLE patients in a phase I-II study (Grouard-Vogel *et al.*, 2014; Lauwers *et al.*, 2013 and 2014). The present trial aims at confirming the promising preliminary biological results and further evaluates the clinical efficacy.

5.2 Background on Systemic Lupus Erythematosus

SLE is a complex autoimmune disease of unknown origin that can affect virtually every organ in the human body but more frequently the skin and mucosa, muscles and joints, the kidneys, the hematopoietic system and the central nervous system. The clinical course of SLE can be highly variable, ranging from a relatively benign illness to a rapidly progressive disease with fulminant organ failure and death. Hallmarks are the accumulation of symptoms and affected organs over time and the undulating disease course characterized by remissions and flares. The prognosis varies in function of the type and severity of the clinical complications, but overall patients with SLE have a nearly 5-fold increased risk of death compared to the general population. The disease is characterized by the presence of numerous autoantibodies against nucleic acid and associated proteins, several of them being associated with the severity of the disease activity.

Worldwide epidemiology studies reported large variations in incidence and prevalence of SLE, reflecting influences of race, ethnicity and socio-economic status (Lisnevskaya *et al.*, 2014; Shim *et al.*, 2014; Nasonov *et al.*, 2014). In 2006, a higher prevalence and incidence were reported for Europe and Australia compared to the USA or to Japan and for individuals of African-American or African-Caribbean descent compared to the white racial group (Danchenko *et al.*, 2006). The worldwide range of incidence (per 100 000 per year) and of prevalence (per 100 000 per year) was 1.6 to 21.9 and 7.4 to 159.4, respectively (Danchenko *et al.*, 2006). In South Korea, the prevalence is approximately 18.8-21.7 per 100 000 (Ju *et al.*, 2014). In France, in 2010, the annual incidence of SLE was 3.3 per 100 000 and the prevalence was 47.0 per 100 000, with higher rates observed in the Caribbean overseas areas than in north-western metropolitan territories (Arnaud *et al.*, 2014).

SLE primarily affects women of childbearing age with a female to male ratio of 9:1 commonly reported, but this predominance is less striking in juvenile and elderly populations.

Treatment of SLE remains unsatisfactory. In many patients, the disease is inadequately controlled, resulting in the progression to end-stage organ failure. Current therapies, such as CS and potent immunosuppressive drugs, which must be administered at high doses, can also lead to serious side effects.

Elevated levels of interferon (IFN)- α in serum have long been recognized to be associated with SLE, both in terms of disease activity and severity (Rönnblom *et al.*, 2006, Bauer *et al.*, 2006, Bauer *et al.*, 2009). Accordingly, patients with SLE also have a dominant pattern of type-1 IFN-inducible gene expression or IFN gene signature (Baechler *et al.*, 2003; Bennett *et al.*, 2003). Yao *et al.* have identified IFN α / β -inducible gene transcripts that are significantly up-regulated in the whole blood of SLE patients (Yao *et al.*, 2009a). By subsequent neutralization with anti-IFNAR or anti-IFN α mabs of healthy mononuclear cells stimulated by SLE serum, they demonstrated that IFN α is mainly responsible for the type I IFN gene signature in SLE patients. They also showed that scoring the IFN gene signature by transcriptomic analyses could serve as biomarker to evaluate the impact of IFN α neutralization. Since then, Phase I and Phase II clinical trials with sifalimumab (an anti-IFN α monoclonal antibody [mab]) (CT.gov# NCT00299819; NCT01283139; NCT01559090), rontalizumab (another anti-IFN α mab) and anifrolumab (an anti-IFNAR mab) have been reported (McBride *et al.*, 2012; Petri *et al.*, 2013; Khamashta *et al.*, 2014; Morehouse *et al.*, 2014). The safety assessment did not reveal any safety concern, there was some indication of positive clinical effect and a significant neutralization of over-expressed IFN α -inducible genes was measured (Yao *et al.*, 2009b; Merrill *et al.*, 2011).

In addition, among a variety of auto-immune and immune-related disorders, SLE has been reported following long term administration of IFN α in patients with malignancies or chronic viral infections (Rönnblom *et al.*, 1991; Ioannou and Ysenberg, 2000; IFN α product information). There is also a correlation between serum IFN α levels and several markers of immune activation typical for SLE such as anti-double-stranded deoxyribonucleic acid (dsDNA) levels, interleukin (IL)-10 levels and a degree of complement activation (Park *et al.*, 1998; Kalsi *et al.*, 1999; Truedsson *et al.*, 2007).

Therefore, this observed association between IFN α and SLE suggests that down-regulation of this cytokine may be beneficial in patients suffering from SLE. An attractive therapeutic strategy is active immunization against IFN α to induce anti-IFN α antibodies to neutralize IFN α biological activity.

